9.7 Exploratory analyses

Descriptive statistics/results from exploratory molecular analyses will be written and may include, but are not limited to: TP53 VAF by NGS, p53 IHC, mutations in other genes by NGS, RNA expression. Please consult Laboratory Manual regarding details on the exploratory biomarker sample processing.

10.0 QUALITY CONTROL AND QUALITY ASSURANCE PROCEDURES

10.1 Monitoring of the Study and Regulatory Compliance

The project manager, or designee, will make an initiation site visit to each institution to review the protocol and its requirements with the Investigator(s), inspect the drug storage area, fully inform the Investigator of his/her responsibilities and the procedures for assuring adequate and correct documentation. During the initiation site visit the CRFs will be reviewed. Other pertinent study materials will also be reviewed with the Investigator's research staff. During the course of the study, the monitor will make regular site visits in order to review protocol compliance, examine CRFs and individual patient's medical records and assure that the study is being conducted according to pertinent regulatory requirements. All CRF entries will be verified with source documentation. The review of medical records will be done in a manner to assure that patient confidentiality is maintained.

10.2 Curricula Vitae and Financial Disclosure of Investigators

All Principal Investigators will be required to provide a current signed and dated curriculum vitae, a completed FDA Form 1572 and a financial disclosure statement to Sponsor's monitoring CRO. All Sub-Investigators will be required to provide a current curriculum vitae and a financial disclosure statement to Sponsor's monitoring CRO.

10.3 Protocol Modifications

No modification of the protocol should be implemented without the prior written approval of the Sponsor or the Sponsor's representative. Any such changes which may affect a patient's treatment or informed consent, especially those increasing potential risks, must receive prior approval by the IRB/IEC. The exception to this is where modifications are necessary to eliminate an immediate hazard to trial patients, or when the change involves only logistical or administrative aspects of the trial (e.g., change in monitor, change in telephone number). Other administrative revisions which may impact the clinical portion of a study will be duly reported to the IRB/IEC by the Principal Investigator.

10.4 Publication Policy

The publication of the results of the study will be subject to the terms and conditions of the clinical trial agreement between the Sponsor and Investigators. Sponsor approval is required for publication of any data from this trial.

11.0 ETHICAL CONSIDERATIONS

11.1 Informed Consent

The Investigator will obtain written informed consent from each patient, or their authorized representative, participating in the study. The form must be signed, witnessed and dated. The informed consent form will contain all the Essential Elements of Informed Consent set forth in 21 CFR, Part 50, the European Union Directive 2001/20/EC and its associated Detailed Guidances, European Union GCP Directive 2005/28/EC, the ICH Guideline for GCP, Section 4.8, and the terms of the Declaration of Helsinki (2013). Copies of the signed document should be given to the patient and filed in the Investigator's study file, as well as the patient's medical record if in conformance with the institution's Standard Operating Procedures.

11.2 Institutional Review Board/Independent Ethics Committee

The study will not be initiated without approval of the appropriate IRB/IEC and compliance with all administrative requirements of the governing body of the institution. This protocol, consent procedures, and any amendments must be approved by the IRB/IEC in compliance with current regulations of the FDA and the European Union as applicable and in accordance with ICH/GCPs. A letter of approval will be sent to the Sponsor prior to initiation of the study and when any subsequent modifications are made. The IRB/IEC will be kept informed by the Investigator, Sponsor's monitoring CRO or the Sponsor, as required by national regulations, as to the progress of the study as well as to any serious and unexpected AEs.

11.3 Patient Privacy

In order to maintain patient confidentiality, all CRFs, study reports and communications relating to the study will identify patients by initials and assigned patient numbers; patients should not be identified by name. In accordance with local, national or federal regulations, the Investigator will allow the Sponsor or designee personnel access to all pertinent medical records in order to verify the data gathered on the CRFs and to audit the data collection process. Regulatory agencies such as the U.S. FDA may also request access to all study records, including source documentation for inspection. Clinical information will not be released without the written permission of the patient as outlined in the patient consent form.

12.0 DATA HANDLING AND RECORD KEEPING

12.1 Data to be Entered Directly in the Case Report Form

The CRF will be the source record.

12.2 Recording of Data

Data collected during the study will be entered in the patient's CRF by the investigational site staff. The staff will keep records of the patient's visit in the files considered as source documents for the site, e.g., hospital chart, research chart. The Investigator will be responsible for the recording of all data on the CRF and for submitting the data to the Sponsor or their designee in a timely manner. Should any value be significantly different from normal, the Investigator will comment in the appropriate sections provided in the CRF.

The Investigator will provide access to his/her original records to permit a representative from the Sponsor to verify the proper transcription of data. To facilitate photocopying, entries must be recorded legibly in black ink only. Erroneous entries will be crossed out with a single line, so as to remain legible. The correct value will be entered above the error and then initialed and dated by the person authorized to make the correction.

12.3 Study Records

U.S. Federal laws require that an Investigator maintain all study records for the indication under investigation for two years following the date a Product Licensing Application is approved or, if no application is to be filed or if the application is not approved for such indication, until two years after the investigation is discontinued and the FDA is notified.


APPENDIX I – Response Criteria Based on Modified Recommendations of the International Working Group for Diagnosis, Standardization of Response Criteria, Treatment Outcomes, and Reporting Standards in Acute Myeloid Leukemia⁵⁹

Response Criterion	Neutrophils, ×10 ⁹ /L	Platelets, ×10 ⁹ /L	Bone Marrow Aspirate Blasts (%) (by biopsy acceptable if aspirate not available)
CR	>1.0	>100	<5
CRI	ANC ≥1,000 OR platelets ≥100,000		<5
MLFS	NA	NA	<5
PR	>1.0	>100	>50% decrease from baseline to level of 5-25%
SD (for patients without a prior best response of CR, CRI, MLFS, or PR)	Absence of CR, CRI, PR, MLFS; and criteria for PD not met		
Hematologic relapse (for patients with a prior best response of CR, CRI, MLFS)	Bone marrow blasts ≥5%, or reappearance of blasts in the blood, on two consecutive assessments separated by ≥28 days. Development of new extramedullary disease.		
PD (for patients with a prior best response of SD or PR)	
Evidence for an increase in bone marrow blast percentage and/or increase of absolute blast counts in the blood, on two consecutive assessments at least 28 days apart:
 
>50% increase in marrow blasts over baseline (a minimum 15% point increase is required in cases with <30% blasts at baseline; or persistent marrow blast percentage of >70% over at least 3 months; without at least a 100% improvement in ANC to an absolute level ($>0.5 \times 10^9/L$ [500/mL], and/or platelet count to $>50 \times 10^9/L$ [50,000/mL] non-transfused); or
 
>50% increase in peripheral blasts (WBC × % blasts) to $>25 \times 10^9/L$ ($>25,000/mL$) (in the absence of differentiation syndrome); or
 
New extramedullary disease
		

Additional Responses to be Assessed in Addition to Above Responses
 
These responses in addition to other responses and do not have specific hematologic criteria.
			
Cytogenetic CR	Normal karyotype in a patient with abnormal cytogenetics at baseline.		

TP53 Molecular CR	TP53 mutation not detected by NGS based on local testing in a patient with detectable TP53 VAF by NGS at baseline.
Additional Responses to be Assessed in Addition to Above Responses These responses in addition to other responses and do not have specific hematologic criteria.	
Cytogenetic CR	Cytogenetic CR
TP53 Molecular CR	TP53 Molecular CR

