5.3 Inclusion Criteria for Patients in Expansion Cohorts

1. Signed ICF and ability to comply with protocol requirements.
2. Newly diagnosed or R/R AML according to WHO classification with permitted prior therapy, as per [Table 3](#). For patients with newly diagnosed AML bone marrow and/or blood evidence of AML with $\geq 20\%$ blasts is required. For patients with newly diagnosed AML, prior therapy with HMA and/or any chemotherapeutic agent for MDS is excluded.
3. Adequate organ function as defined by the following laboratory values:
 - a. Creatinine clearance > 30 mL/min (by Cockcroft-Gault method; [APPENDIX II](#)),
 - b. Total serum bilirubin $< 1.5 \times$ ULN unless due to Gilbert's syndrome, leukemic organ involvement, hemolysis or considered an effect of regular blood transfusions,
 - c. ALT and AST $< 3 \times$ ULN, unless due to leukemic organ involvement.
4. Age ≥ 18 years at the time of signing the ICF.
5. At least one *TP53* mutation which is not benign or likely benign, based on central *TP53* testing results. If local *TP53* mutation and/or p53 IHC results become available before central *TP53* mutation results, enrollment may be made based on local results with Medical Monitor approval.
6. ECOG performance status of 0, 1 or 2 ([APPENDIX III](#)).
7. Projected life expectancy of ≥ 12 weeks.
8. Negative serum or urine pregnancy test prior to study treatment initiation in female patients of childbearing potential.
9. Females of childbearing potential and males with female partners of childbearing potential must be willing to use an effective form of contraception such as latex condom, hormonal birth control, intrauterine device or double barrier method ([APPENDIX IV](#)) during chemotherapy treatment and for at least six months thereafter.

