6.4 Concomitant Treatment

Patients must not receive any other concurrent anti-cancer therapy, including investigational agents while on study treatment. Please also see Section 2.3, regarding known drug-drug interactions for venetoclax, and the importance of avoiding certain food such as grapefruits. This is important both for patient safety and for enabling a correct assessment of an unlikely drug-drug interaction between the study drug APR-246 and venetoclax. For patients concomitantly treated with strong or moderate CYP3A inhibitors, or P-gp inhibitors, the dose of venetoclax should be determined based on institutional practice and current prescribing information. Strong or moderate CYP3A inducers should be avoided (see [APPENDIX VIII](#)).

Patients may continue their baseline medication(s) as long as they are not prohibited. Palliative and supportive care (e.g., anti-emetics, bisphosphonates) for disease-related symptoms will be offered to all patients in the study per institutional practices. AEs will be treated as clinically indicated. All concomitant medications that are currently in use or that become necessary during the study should be recorded.

If the patient develops an acute infusion reaction (\geq Grade 2), the infusion must be stopped until the reaction is resolved to \leq Grade 1. Premedication (e.g., systemic corticosteroids) may be used after the first cycle.

Use of myeloid growth factors is allowed at the discretion of the investigator per institutional practices. If patients experience prolonged myelosuppression, they should be placed on infection prophylaxis per standard of care.

Hydroxyurea may be used for control of leukocytosis.

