- k. Initial response assessment (blasts percentage) is performed on Day 22 (± 3 days). In patients with bone marrow hypocellularity, venetoclax may need to be held and restarted after recovery of blood counts (ANC $\geq 0.5 \times 10^9/L$, and platelets $\geq 25 \times 10^9/L$), confirmed by repeat bone marrow biopsy on approximately Day 35 and following discussion with Medical Monitor. For subjects who

require a delay in study treatment for peripheral blood count recovery after a bone marrow evaluation, hematology values for up to 4 weeks from the bone marrow analysis can be used to determine the IWG response. Ongoing response assessments should be performed at the end of each cycle (every 4 weeks) starting at Cycle 2, based on peripheral blood and bone marrow sample (at the end of even cycles), and peripheral blood sample alone (at the end of odd cycles). After the first year of the study treatment response assessment will be performed every two months. Following a documented CR, a bone marrow aspirate/biopsy is not required if the response assessment can be made based on the peripheral blood, except at the time of suspected relapse at which time a bone marrow aspirate/biopsy is required.

- I. Hematology, including complete blood count with white blood cell differential, weekly. Additional peripheral blood sample should be collected on Day 1 of each cycle starting at Cycle 2 for disease assessment, if bone marrow aspirate is not available.
- m. Serum chemistry, including sodium, potassium, chloride, magnesium, CO₂, blood urea nitrogen (BUN), creatinine, glucose, calcium, albumin, total protein, total bilirubin, AST, ALT, alkaline phosphatase weekly. At screening, the creatinine clearance may be calculated from the serum creatinine. A 24-hour urine for creatinine clearance may be performed at Investigator's discretion.
- n. Serum or urine β hCG must be performed within 7 days prior to study treatment initiation in female patients of childbearing potential.
- o. Standard 12-lead ECGs in triplicate at screening, on Days 1–4 of Cycle 1 and on Days 1 of each subsequent cycle with patient in a semi-recumbent position. Please consult [Table 12](#) for ECG collection schedule.
- p. *Only in cohorts with venetoclax:* Potassium, phosphorus, calcium and uric acid should be evaluated approximately 6–8 hr and 24 hr (\pm 4 hr) after the initial administration of venetoclax in order to monitor for potential development of TLS.

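### Appendix I response rows test only marrow blasts and counts, so a patient with persisting blood blasts or baseline extramedullary disease can be scored a responder

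*Combined protocol and SAP*

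**What the plan says.** The Appendix I response rows set these conditions:

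- CR: "CR >1.0 >100 <5", that is neutrophils, platelets and marrow blasts.
- CRi: "ANC ≥1,000 OR platelets ≥100,000", with marrow blasts below 5%.
- MLFS: marrow blasts below 5%, with both count columns marked not applicable.
- SD: none of CR, CRi, PR or MLFS is met, and PD is not met.

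The failure rows of the same table look further. Relapse, for patients whose best response was CR, CRi or MLFS, includes "reappearance of blasts in the blood, on two consecutive assessments separated by" at least 28 days, and also "Development of new extramedullary disease". The PD row, for patients whose best response was SD or PR, uses peripheral blasts and new extramedullary disease, and recognises a platelet improvement only if it is "50,000/mL] non-transfused".

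Section 9.3.2 counts MLFS in ORR and defines CRh by marrow blasts, ANC and platelets only. On entry to the expansion cohorts, Section 5.3 reads "For patients with newly diagnosed AML bone marrow and/or blood evidence of AML with" at least 20% blasts. No such floor is stated for relapsed or refractory (R/R) AML. The only extramedullary site that Section 5.4 excludes is active CNS involvement.

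**The concern.** The table treats circulating blasts, extramedullary disease and transfused platelets as relevant to whether a patient has failed, but not to whether the patient has responded. CR, CR+CRi, CR+CRh and ORR all rest on these rows or on the parallel CRh definition. If the rows are applied as written, a patient with visible leukaemia outside the marrow enters the numerator. The error can add responders to these four rates but cannot remove them, and the cohorts are small and open-label.

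**Working it through.** The plan's one calculation that uses a response rate is the two-stage design in Section 9.1: continue if more than 4 of 18 respond, succeed at 11 or more of 33, with a 20% null and a 40% target. It reproduces by exact binomial calculation, with type I error 0.046 and power 0.801. This point does not dispute it and takes no magnitude from it. The rest is a reading of the rules.

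**Rows side by side** (counts ×10⁹/L; a dash means no condition stated)

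| Category | Counts | Marrow blasts | Blood blasts | Extramedullary disease | Transfusion |
|---|---|---|---|---|---|
| CR | ANC >1.0 and platelets >100 | <5% | – | – | – |
| CRi | one of the two thresholds | <5% | – | – | – |
| CRh (9.3.2) | ANC >0.5 and platelets >50 | <5% | – | – | – |
| MLFS | not applicable | <5% | – | – | – |
| PR | ANC >1.0 and platelets >100 | >50% fall, to 5–25% | – | – | – |
| Relapse | – | ≥5% | reappearance | new | – |
| PD | lack of ANC and/or platelet improvement | >50% rise, or persistently >70% | >50% rise, to >25 | new | platelets non-transfused |

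**Case 1: marrow below 5%, blood blasts never cleared, counts below every threshold.**
1. CR, CRi and CRh fail on counts. MLFS is met.
2. SD is unavailable, because it requires MLFS to be absent.
3. PD is unavailable, because that row covers only a prior best response of SD or PR.
4. The patient is MLFS and counts in ORR.
5. For relapse, blasts that never disappeared cannot literally reappear. Only marrow blasts of 5% or more, or new extramedullary disease, ends the response.

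With adequate counts the same patient is scored CR, CRi or CRh.

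**Case 2: marrow below 5%, extramedullary disease present at baseline and persisting.** The route is the same. The relapse row catches only new extramedullary disease.

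**Case 3: platelet threshold met only through transfusion.**
- Marrow below 5% and ANC >1.0: CR instead of CRi. ORR is unchanged.
- Marrow below 5% and ANC below 1.0: CRi instead of MLFS. ORR is unchanged.
- Marrow below 5% and ANC >0.5: the patient can also be moved into CRh. ORR is unchanged.
- Marrow 5–25% after a fall of more than 50%, and ANC >1.0: PR instead of SD. ORR rises.

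**Case 4: R/R entry.** Section 5.3 asks for R/R AML by WHO classification with permitted prior therapy. No marrow floor is stated for these patients and MLFS has no baseline condition, so a patient entering Cohort 3 or 4 with marrow below 5% meets MLFS before the first dose.

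**Size.** If m of n patients in a cohort are scored as responders only through these gaps, the reported rate exceeds the intended rate by m/n. The documents give no value for m. As an assumed range, m/n of 0%, 5% or 10% adds 0, 5 or 10 percentage points.

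**The case against.** The best defence is that the rule is incompletely written and was never meant to count circulating leukaemia as remission. ORR is defined by the IWG 2003 criteria, blood blast percentage is assessed at the end of odd cycles (Section 7.2.4), and the word for reappearance implies that clearance was expected. The intent is plausible. However, Appendix I is the definition the endpoints cite, it is headed as a modified version, and nothing in it carries over unlisted conditions. Sections 7.1 and 7.2.4 say that blood is examined, not how the result enters CR, CRi or MLFS.

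It is also fair that these are secondary endpoints of a Phase I trial with safety primaries, and that Section 9.5 plans no formal comparison of CR rate between arms. That limits the weight of the point.

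A reader might infer more than the documents support:

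- **That R/R patients do enter already in MLFS.** They can; no baseline marrow data are given. The relapse row governs on-study responders, not eligibility.
- **That the two-stage decision in Cohorts 2 and 5 is compromised.** Those cohorts are front line, so the R/R entry gap concerns other cohorts, and Section 9.1 does not say which response the design counts. One patient crossing a boundary would not measure this defect.
- **That duration of response is always lengthened.** Uncleared blood blasts escape the relapse wording. But scoring MLFS also moves the patient from the PD rule to the relapse rule, where marrow blasts of 5% on two assessments suffice. The net direction is not established.
- **That growth-factor support is handled inconsistently.** Section 6.4 says "Use of myeloid growth factors is allowed at the discretion of the investigator per institutional practices", but the PD row speaks only of transfusion. Excluding growth-factor-supported counts would be a preference, not a correction of a contradiction.
- **That a Day 22 marrow needs confirmation under Table 8, footnote k.** The text, "In patients with bone marrow hypocellularity, venetoclax may need to be held and restarted after recovery of blood counts", governs holding and restarting treatment. It is not a response-confirmation rule.

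**Conclusion.** The point holds as a defect in stated rules, not merely as missing detail: the SD row forces Cases 1 and 2 into a response category. The blood-blast and baseline extramedullary gaps affect ORR, and also CR, CR+CRi and CR+CRh when counts suffice. The transfusion gap affects CR, CRi, CRh and PR, and reaches ORR only through PR. The baseline overlap is a possibility in Cohorts 3 and 4. The direction is favourable for all four response rates; the size is unknown and could be zero. The conclusion rests on applying Appendix I and Section 9.3.2 as written, without importing conditions from the cited source. The change should be made, in proportion to secondary endpoints.

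**What to change.** 1. Add a condition of no blasts in peripheral blood and no extramedullary disease to CR, CRi and MLFS in Appendix I, and to CRh in Section 9.3.2.
2. Require the platelet thresholds for CR, CRi, CRh and PR to be met without transfusion, as the PD row already does, and state one transfusion-free interval for all four.
3. Where baseline marrow blasts were below 5%, do not score MLFS on marrow blasts alone. Require clearance of the blood or extramedullary disease present at baseline.

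The cost is wording in two places and slightly lower reported response rates. Differentials and physical examinations are already scheduled, and transfusion data are needed for the transfusion-independence endpoint. The study calendar has no separate row for transfusions or for extramedullary assessment, so the sponsor should confirm that the CRF captures transfusion dates and baseline extramedullary sites. No change to treatment is involved.

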APPENDIX II - Cockcroft-Gault Equation

Males:

$$\text{Creatinine CL} = \frac{\text{Weight (kg)} \times (140 - \text{Age})}{72 \times \text{serum creatinine (mg/dL)}}$$

Females:

$$\text{Creatinine CL} = \frac{\text{Weight (kg)} \times (140 - \text{Age}) \times 0.85}{72 \times \text{serum creatinine (mg/dL)}}$$

APPENDIX III - ECOG Performance Status

Grade	
0	Fully active, able to carry on all pre-disease performance without restriction.
1	Restricted in physically strenuous activity but ambulatory and able to carry out work of a light or sedentary nature, e.g., light housework, office work.
2	Ambulatory and capable of all self-care but unable to carry out any work activities. Up and about more than 50% of waking hours.
3	Capable of only limited self-care, confined to bed or chair more than 50% of waking hours.
4	Completely disabled. Cannot carry on any self-care. Totally confined to bed or chair.
5	Dead.

